# **Safety and Effectiveness of the Treatment of Wide Neck, Saccular Intracranial Aneurysms with the Neuroform Atlas™ Stent System**

## **Short Study Name: ATLAS**

### **4.4 Analysis Populations**

**ITT (Intent to Treat):** All subjects who have signed the Informed Consent Form for this trial, and in whom the Neuroform Atlas™ Stent implantation procedure has been attempted (i.e., a component of the stent system was introduced into the body).

**mITT (Modified Intent to Treat):** All subjects who have signed the Informed Consent Form for this trial, and in whom the Neuroform Atlas™ Stent has been successfully implanted.

**PP (Per Protocol):** All subjects who have signed the Informed Consent Form for this trial, who have had the Neuroform Atlas™ Stent successfully implanted, and who have not been the subject of any major protocol deviations.

**Enrolled Not Treated:** All subjects who have signed the Informed Consent Form for this trial, but in whom no component of the Neuroform Atlas™ Stent System has ever been introduced into the body as part of an implantation procedure.

**PAS ITT (ITT for the PAS):** All subjects who have signed the Informed Consent Form for this trial, and in whom the Neuroform™ Atlas Stent has been successfully implanted. This cohort is identical to the mITT cohort.

**PAS mITT (Modified Intent to Treat in PAS):** All mITT subjects who have not withdrawn, died, or refused follow-up.

The primary safety and effectiveness analyses will be performed on the mITT population. The 95% Confidence Interval (CI) for each endpoint will be calculated using the exact binomial distribution. In addition, safety data will include any adverse events reported to occur among ITT subjects in whom a Neuroform Atlas™ Stent implantation procedure was attempted but did not successfully occur. For long-term follow-up, all analyses completed for the PAS mITT cohort will also be completed for the PAS ITT cohort for comparison

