**Short Study Name: ATLAS**

**Table 7 – Endpoint Measure Definitions in the Post-approval Study**

	Survival Analysis		Incidence Rate		% Subjects who Experienced the Outcome [2]			
	Competing Risk [1]	Event	Numerator	Denominator	Numerator	Denominator		
Primary Safety Outcome	Non-neurologic death	Death	Number of events (N1)	Person-time based on follow-up date (D1)	Number of subjects who experienced new outcome in the interval (N2)	Number of subjects present for one or more visits during or after the interval or experienced outcomes during the interval (D2)		
Neurological death								
New or worsening major ipsilateral stroke								
Any ischemic or hemorrhagic AE(s)								
Hemorrhagic Stroke								
Ischemic Stroke								
SAH								
Aneurysm Rupture								
TIA								
Device-related SAE(s)								
Grade 1 Raymond class in the absence of retreatment, or parent artery stenosis (>50%) at the target location	N/A	N/A	N/A	N/A	Number of subjects who are not retreated and whose current DSA met the outcome definition	Number of subjects with valid DSA or underwent retreatment		
Retreatment	Death	The first event	N1	D1	N2	D2		
Raymond Class	N/A	N/A	N/A	N/A	Number of subjects whose current DSA met the outcome definition	Number of subjects with valid DSA		
Parent Artery Stenosis > 50%	N/A	N/A	N/A	N/A				
Recanalization	Death	The first event	N1	Person-time based on DSA date				
Stent Migration								
Progressive Occlusion of the Target Aneurysm	N/A	N/A	N/A	N/A				

[1] Subjects are censored on the date of the event; other censoring events include lost-to-follow-up, consent withdrawal, and study early discontinuations due to other reasons.

[2] Repeated for each visit interval, i.e. 2-year, 3-year, post-3-year intervals.

[3] The observational period for the survival analysis and incidence rate starts on the day after a subject's 12-month follow-up visit.

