## **4.8 Follow-up and Reporting**

All subjects enrolled and devices used in the clinical investigation will be accounted for in the final report. All reasons for exclusion from analysis will be documented. Similarly, for all subjects and devices included in an analysis population, the measurements of all important variables will be accounted for at all relevant time points.

Subjects lost to follow-up or withdrawn from the study will be identified, and a descriptive analysis of them will be provided, including the reasons for their loss to follow-up and known treatment outcomes.

All PAS mITT subjects will be asked to return for a 2-year visit and a 3-year visit. If the 3-year visit window has elapsed at the initiation of the PAS follow-up, subjects will be asked to return for at least one long-term follow-up visit.

The analysis of long-term safety and effectiveness data will be descriptive only, as no formal hypotheses will be tested based on data collected during this phase of the study. Survival analysis will be used to estimate the incidence of specified safety endpoint events, as well as retreatment of the target aneurysm.

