## **4.9 Assessment of Attrition Bias**

Differential attrition rates among subgroups of the ATLAS subjects could potentially bias the observed safety and durability status in both directions. Adverse events may prevent patients from adequately participating in the study, i.e., informative censorings are created. On the other hand, certain tests may be biased due to the under-participation of the healthier subgroup. Adverse events may result in more frequent hospital visits and therefore a better chance to report mRS and NIHSS. Difficult-to-treat aneurysms with suboptimal occlusion status may be more likely to undergo additional angiograms and to be evaluated with the Raymond-Roy scale.

Analyses will be performed at various stages of the PAS to evaluate the potential effects of attrition bias. Since subjects who died, withdrew, or are lost to follow-up can no longer be followed in the PAS, statistics reported for the PAS mITT cohort should be interpreted as conditional on a given subject's

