# **Safety and Effectiveness of the Treatment of Wide Neck, Saccular Intracranial Aneurysms with the Neuroform Atlas™ Stent System**

## **Short Study Name: ATLAS**

survival of the first 12 months after the procedure. At the initiation of the PAS, summary statistics on demographics and key clinical characteristics at 12-month follow-up visits will be compared between cohorts with and without deaths, withdrawals, and loss to follow-up. Once patient enrollment for the PAS begins, we will update the PAS mITT cohort with the actual enrollment and present the updated comparison in the interim progress reports and final report.. Sensitivity analyses will be carried out based on different assumptions of the pattern of loss to follow-up. Raymond-Roy scale and mRS will be reported within the context of previous test results. All analyses performed on the PAS mITT cohort will be compared to the PAS ITT population.

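### If PAS mITT status is judged at PAS enrolment, as Sections 4.8 and 4.9 imply, Table 7 counts time in which no member can have died, and the neurological-death rate is biased low

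*Combined protocol and SAP*

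**What the plan says.** **Time origin.** In Table 7 (Section 4.6), note [3] reads "The observational period for the survival analysis and incidence rate starts on the day after a" subject's 12-month follow-up visit. The incidence-rate denominator is person-time to the follow-up date. Delayed entry is not mentioned.

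**Interval percentages.** The Table 7 denominator D2 is "Number of subjects present for one or more visits during or after the interval or experienced outcomes during the interval".

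**Population.** Section 4.4 defines PAS mITT as "All mITT subjects who have not withdrawn, died, or refused follow-up" and does not say when this is judged. PAS ITT is the whole mITT population, and PAS mITT analyses are repeated in it for comparison.

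**When status appears to be judged.**
- Section 4.8: "All PAS mITT subjects will be asked to return for a 2-year visit and a 3-year visit".
- Section 4.9: "subjects who died, withdrew, or are lost to follow-up can no longer be followed in the PAS".
- Section 4.9: at PAS initiation, 12-month characteristics "will be compared between cohorts with and without deaths, withdrawals, and loss to follow-up".
- Section 4.9: once PAS enrolment begins, "we will update the PAS mITT cohort with the actual enrollment".

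**A sentence pointing the other way.** Section 4.9 also says that PAS mITT statistics are conditional on "survival of the first 12 months after the procedure".

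**Timing.** Table 1 dates the start of PAS patient enrolment at 31 March 2020. A Table 2 footnote provides for subjects whose procedure was 43 to 60 months before PAS enrolment.

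**The concern.** A subject must be alive at PAS enrolment to belong to a cohort defined by PAS enrolment. The time between the 12-month visit and enrolment is therefore death-free by construction. Counting it as time at risk adds to the denominator and can add nothing to the numerator (immortal time).

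D2 has the same fault. A subject first seen after month 42 was present after the 2-year and 3-year intervals, and so enters both denominators although death in those intervals would have kept that subject out of the cohort. D2's clause for subjects with outcomes in the interval does not help, because someone who died before enrolment is not in the population to be counted.

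Neurological death is part of the safety outcome that the PAS continues to collect (Sections 2.3.3 and 4.6.3). Its long-term rate would be understated, and Section 4.9 would give the reader a weaker condition than the real one, which is survival to, and participation at, PAS enrolment.

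**Working it through.** The plan states no long-term death rate, person-time or distribution of PAS entry, so there is no figure to reproduce.

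**Inputs**
- Start of counted time: month 12 (Table 7, note [3]).
- PAS entry at month E: distribution not given; E is varied.
- End of follow-up at month F: 36 + 6 = 42 (Section 2.1). For entry at months 43 to 60, one visit is enough (Section 4.8), so F can equal E.
- Death-free time counted for those late entrants: 43 − 12 = 31 to 60 − 12 = 48 months.
- Hazard of neurological death: not given; assumed constant at 0.5%, 1% and 2% per year.
- Fatal share q of the composite: 1/17 from the MAPS cohort (Table 5: one neurological death; 12 + 5 = 17 composite events). The text of Section 4.5.2 counts 18, which gives the same result to two decimals. MAPS counted strokes of any severity, so the share for major stroke may differ; 0.25 and 0.5 are added as assumptions.

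**Death rate.** Let g = E − 12 and f = F − E. Among members alive at E with a low hazard λ, expected deaths are about λf and counted time is about g + f. Estimated over true rate is therefore about f/(g + f).

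**Composite.** If every stroke in the gap among survivors is captured, only the fatal part shrinks: (1 − q) + q·f/(g + f) = 1 − q·g/(g + f).

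| PAS entry | g | f | Death rate | Composite, q = 1/17 | q = 0.25 | q = 0.5 |
|---|---|---|---|---|---|---|
| Month 18 | 6 | 24 | 24/30 = 0.80 | 0.99 | 0.95 | 0.90 |
| Month 24 | 12 | 18 | 18/30 = 0.60 | 0.98 | 0.90 | 0.80 |
| Month 30 | 18 | 12 | 12/30 = 0.40 | 0.96 | 0.85 | 0.70 |
| Months 43–60, one visit at enrolment | 31–48 | 0 | 0 | 0.94 | 0.75 | 0.50 |

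Entries are ratios of estimated to true rate. Entry at month 12 gives 1.00.

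**Check of the approximation.** Exact exponential ratios at 0.5%, 1% and 2% per year are 0.799, 0.798 and 0.797 (entry at month 18); 0.599, 0.598 and 0.596 (month 24); 0.399, 0.399 and 0.398 (month 30).

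**Simulation.** 2,000,000 subjects, true rate 1.00% per year, entry spread uniformly, follow-up to month 42 or to the single visit if later:

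| Entry months | Rule as written | Delayed entry | 12-month cohort, all deaths counted |
|---|---|---|---|
| 12–24 | 0.80% | 1.00% | 1.00% |
| 18–36 | 0.50% | 1.00% | 1.00% |
| 24–48 | 0.22% | 1.00% | 1.00% |

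**D2.** The 2-year window ends at month 24 + 6 = 30. If a share s of the 2-year denominator enrolled after month 30, those subjects contribute no deaths, and the 2-year death percentage is multiplied by at most 1 − s.

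**The case against.** The best reply is that Section 4.9 states the conditioning outright, as survival of the first 12 months. That agrees with note [3]. If PAS mITT status is fixed at the 12-month visit and later deaths are counted, there is no immortal time. This stands as a possible intention, and it is why the point is conditional. It does not settle the matter, because the same section then updates the cohort with actual enrolment, which a cohort fixed at month 12 would not need.

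The plan also has safeguards. It repeats every analysis in PAS ITT, compares subjects with and without deaths and losses, names informative censoring, promises sensitivity analyses on the pattern of loss to follow-up, and requires contact attempts that may include next of kin (Section 3.4). These can expose the problem. None of them moves the start of risk time or corrects the PAS mITT figure. PAS ITT is sound only if gap deaths are traced. Section 4.7 censors lost subjects at last contact, so an untraced death contributes neither an event nor gap time, while those who enrol contribute their whole gap.

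A reader might infer that note [3] is wrong in itself. It is not: month 12 is the right origin for PAS ITT.

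A reader might also infer that all PAS safety rates are too low. The documents do not support that. Non-fatal gap events can be recovered by chart review (Table 2 footnote), and Section 4.9 recognises that attrition bias may go either way.

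**Conclusion.** The point holds on the reading that Sections 4.8 and 4.9 best support, namely that PAS mITT membership requires being alive and enrolled in the PAS. The rules in Table 7 then bias the PAS mITT neurological-death rate downward whenever the gap and the hazard exceed zero. Section 4.9's statement about 12 months conflicts with its own enrolment update.

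Only the direction is certain. The ratios of 0.80, 0.60, 0.40 and about 0 rest on a low constant hazard, follow-up ending at month 42, and the assumed entry months. For the composite the loss may be slight (0.94 at worst at the MAPS share) or material (down to 0.50 if half the events were fatal and all subjects were late single-visit entrants).

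A reader might try to derive one overall factor from the Table 1 dates, taking follow-up as 31 March 2020 to 31 August 2021. The documents do not support that: the dates are milestones rather than observed entry dates, and 17 months from entry at month 30 would run to month 47, past the 42-month limit.

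Nor does the point reach the 12-month endpoints or any success criterion. The PAS is descriptive, but a descriptive rate is what it delivers, so the bias is worth removing.

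**What to change.** Choose one consistent rule and state the date at which PAS mITT status is taken.

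1. **Preferred.** Make PAS ITT, or a PAS mITT fixed at the 12-month visit, the main analysis of neurological death and of the composite, with the month-12 origin. Trace vital status through the Section 3.4 contacts and through records where consent permits (Sections 2.6.3 and 3.3 limit this for withdrawn subjects). Report the number with unknown vital status.
2. **If PAS mITT is defined by PAS enrolment.** Use delayed entry (left truncation) at enrolment for death. Count a subject in D2 for death only in intervals that begin on or after enrolment, or replace D2 by person-time within the interval. Requiring only that the interval end after enrolment is not enough: someone enrolled at month 29 would count in the whole interval from month 18 to 30, of which 11 of 12 months were death-free.
3. **Composite.** Take the 12-month-to-3-year composite from PAS ITT or the 12-month cohort. Restarting it at enrolment would depart from the objective in Sections 2.3.3 and 4.6.3.
4. **Section 4.9.** State the conditioning that actually applies.

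The cost is one enrolment-date variable, some SAP wording and record review for subjects who do not enrol. Delayed entry gives less person-time and wider intervals for death in PAS mITT; single-visit subjects add almost nothing there. It also does not remove selection through refusal. PAS ITT will carry some unknown vital status.

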### **1.7 Duration of the Study**

It is anticipated that the enrollment of a maximum of 360 subjects in this pivotal trial will take approximately 40 months at up to 40 centers. Evaluation of the primary safety and effectiveness endpoints will be completed on all subjects at 12 months. The time required to complete enrollment of up to 360 subjects and 12 month follow up for all study subjects is anticipated to take approximately 52 months.

Evaluation of long-term safety will continue through 3-year ( $\pm 6$  months) follow-up. Inclusive of long-term follow-up it is anticipated the entire duration of the study, from the date the first subject enrolled into the IDE study through the date the last subject completed a 3-year PAS follow-up visit, will be approximately 6 years (the PAS phase of the study is anticipated to last 24 months). To allow adequate monitoring of PAS progress, PAS study milestones are summarized in **Table 1**.

**Safety and Effectiveness of the Treatment of Wide Neck, Saccular Intracranial Aneurysms with the Neuroform Atlas™ Stent System**

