### **3.2 Informed Consent**

Subjects will be informed by the Investigator or the Investigator's designee that they are free to refuse participation in this research study. If they elect to participate, it will be made clear that they may withdraw from the study at any time without prejudicing further care.

The Investigator or the Investigator's designee will inform subjects that their medical records will be subject to review by the Sponsor or appropriate regulatory bodies. This information will be used during the analysis of the results of the clinical study, but the subjects' identities will be treated as confidential. Subjects will be assigned a unique identification code. This code will be used on all data and data collection forms during the study period. It will not reveal the subject's identity.

The Investigator will explain the conditions of the study, giving the subject sufficient time to ask questions and to consider whether or not they want to participate. Subjects will be informed that active study participation is expected through their 12-month follow-up visit, but the informed consent form will allow for continued follow-up through 60 months post-treatment should longer term follow-up

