\*\*\* Hunt and Hess scoring will be performed only when evaluating subjects who have evidence of subarachnoid hemorrhage.

\*\*\*\* Pre-implant angiography (MRA, CTA, or DSA) may be performed up to 6 months prior to treatment. In addition to the post-implant and 12 month angiographic studies, it is recommended that an imaging study be performed within 24 hours of the onset of symptoms in any treated subject suspected of having a stroke. Although not required, if it is standard of care to do so at a given Clinical Trial Site, imaging (MRA or DSA) may be performed at the 2- or 6-month follow-up visit or per standard of care at each institution for the 2 and 3 years long term follow up visit.

∞ At 2-year, 3-year, and post 3-year follow-up, NIHSS, mRS and neurological exams will be collected if performed. For any suspected stroke events that occur in the PAS, NIHSS will be collected at the time of event and at 24 hours post event; mRS will be collected at discharge from event and at a minimum of 90 days post event. For any aneurysm rupture case, Hunt and Hess grade will be performed or collected if available. Any imaging performed due to suspected stroke event will be submitted to the sponsor. AEs can be collected via retrospective chart review, phone calls or in-person visits and will include all the new and ongoing adverse events.

£ At least one (1) ATLAS PAS visit will be conducted in-person.

**STRYKER CONFIDENTIAL - THIS DOCUMENT CONTAINS CONFIDENTIAL AND PROPRIETARY INFORMATION THAT IS THE PROPERTY OF STRYKER CORPORATION. NEITHER THIS DOCUMENT NOR THE INFORMATION HEREIN MAY BE REPRODUCED, USED, OR DISCLOSED TO ANY THIRD PARTY WITHOUT THE PRIOR WRITTEN CONSENT OF STRYKER CORPORATION.**

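### Table 7's single long-term safety rate pools look-back time before the post-approval study with follow-up inside it, and is likely low for TIA, minor events and major-stroke grading

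*Combined protocol and SAP*

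**What the plan says.** - **Start of the clock (Section 4.6, Table 7, note [3]).** "The observational period for the survival analysis and incidence rate starts on the day after a subject's 12-month follow-up visit". Each safety row divides the number of events (N1) by one person-time total (D1), with no division by how that time was observed. Percentages of subjects are also given for the 2-year, 3-year and post-3-year intervals.
- **Follow-up before the PAS.** Section 3.2 states: "Subjects will be informed that active study participation is expected through their 12-month follow-up visit". It adds that consent allows follow-up to 60 months if needed. Table 1 puts the first PAS follow-up at 31 March 2020. No contact is scheduled between a subject's 12-month visit and the PAS.
- **How later events are found (Table 2 footnotes).** "AEs can be collected via retrospective chart review, phone calls or in-person visits". Sections 3.10 and 6.1 make clear that events since the last visit are meant to be captured.
- **Stroke grading.** The Table 2 footnotes say: "For any suspected stroke events that occur in the PAS, NIHSS will be collected at the time of event", and again at 24 hours. Section 2.4.1.2 defines a major ipsilateral stroke by an NIHSS rise of at least 4 at 24 hours.
- **Timeline (Section 1.7).** "enrollment of a maximum of 360 subjects in this pivotal trial will take approximately 40 months at up to 40 centers"; enrolment plus 12-month follow-up "is anticipated to take approximately 52 months"; the whole study lasts about 6 years, and "the PAS phase of the study is anticipated to last 24 months".

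**The concern.** A pooled incidence rate is easy to read only if events are found about equally well throughout the denominator. Here the denominator has two parts. From the 12-month visit to PAS enrolment, an event enters the numerator only if a chart, a telephone call or a later visit brings it to light. From PAS enrolment onward, the stroke work-up is specified.

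The look-back can be long. Table 2 has a column for subjects 43–60 months from the index procedure at PAS enrolment. Counted from a nominal 12-month visit, that is 31–48 months to reconstruct, possibly at one visit. The outcomes include TIA, which Appendix B limits to 24 hours or less, and ischemic or hemorrhagic events of any severity. A gap-period stroke without a 24-hour NIHSS cannot be graded against the definition and may drop out of the primary safety row. These rates are the long-term safety output reported to FDA, and one pooled figure hides the mixture.

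**Working it through.** The documents state no person-time split, so it has to be built from the planned timeline.

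**1. Reproduce the plan's figure.** 40 months' enrolment + 12 months' follow-up = 52 months, as Section 1.7 states. 52 + 24 = 76 months (6.3 years), against about 6 years (72 months). Working back from 72, the PAS starts at month 72 − 24 = 48.

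**2. Section 1.7 timeline.** Assume uniform enrolment over months 0–40. At month 48, time since index *t* is uniform on 8–48 months.
- Pre-PAS time = max(0, *t* − 12). Mean = (36² / 2) / 40 = 16.2 months.
- Total time = 24 months if *t* < 36 (28/40 of subjects). Otherwise it is *t* − 12 plus a wait *d* for one PAS visit (12/40 of subjects, mean *t* − 12 = 30). Mean = 0.7 × 24 + 0.3 × (30 + *d*) = 25.8 + 0.3*d*.
- Share before the PAS: 16.2/25.8 = 62.8% (*d* = 0); 16.2/26.7 = 60.7% (3); 16.2/27.6 = 58.7% (6); 16.2/29.4 = 55.1% (12).

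**3. Table 1 dates.** The last in-person 3-year visit is due 30 June 2021. If it falls at 30 months, the earliest point of the window, the last index procedure was at the end of 2018, 15 months before 31 March 2020. So *t* is uniform on 15–55.
- Mean pre-PAS time = 35 − 12 = 23.0 months.
- Mean total = 0.525 × 24 + 0.475 × (33.5 + *d*) = 28.5 + 0.475*d*.
- Share before the PAS: 76.8% (*d* = 3), 73.3% (6), 67.2% (12).

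**4. Wider timeline assumptions.** First index procedure 72 months before 31 August 2021, follow-up capped at that date. Cells give mean pre-PAS months / mean total months.

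| PAS start | Last contact at 3-year visit | Last contact at month 42 | All followed to 31 Aug 2021 |
|---|---|---|---|
| Month 48 (24-month PAS) | 16.2/25.6 = 63% | 16.2/29.2 = 55% | 16.2/40.0 = 41% |
| Month 53 (31 Jan 2020) | 21.0/27.4 = 77% | 21.0/30.3 = 69% | 21.0/40.0 = 53% |
| Month 55 (31 Mar 2020) | 23.0/28.3 = 81% | 23.0/30.9 = 75% | 23.0/40.0 = 58% |
| Month 61 (30 Sep 2020, last IRB approval) | 29.0/31.6 = 92% | 29.0/33.3 = 87% | 29.0/40.0 = 73% |

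The range is 41–92%. Reading the timeline as a PAS from month 52 to month 76 gives 45–74%, inside that range. The right-hand column follows the earliest subjects to 72 months, beyond any visit in Table 2, so it is a lower bound rather than a likely case.

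**5. Effect on a rate.** Let *w* be the pre-PAS share and *s* the fraction of gap events that look-back finds and can grade, relative to PAS follow-up. With the same true event rate in both periods, observed/true = 1 − *w*(1 − *s*). The documents give no *s*; the values below are assumptions.

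| Assumed *s* | Shortfall at *w* = 55–63% |
|---|---|
| 100% | 0 |
| 80% | 11–13% |
| 70% | 17–19% |
| 50% | 28–31% |

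At *w* = 55.1%, the shortfall passes 10% when *s* is below 1 − 0.10/0.551 = 82%.

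**The case against.** A reader might infer that nobody was followed before the PAS, that no 24-hour NIHSS exists for that time, and that the rates are therefore biased low by a known amount. The documents do not support this. Section 6.1 has adverse events collected from enrolment through 3 years. Section 3.10 has each PAS visit record events since the previous one, and Section 10.2 provides for adjudication through the end of the PAS. Table 2 and Section 3.11 provide for an NIHSS at unscheduled visits in defined circumstances. A 24-hour value was not required for gap strokes, but one may be in the chart. The numerator is meant to cover the gap, so the issue is quality of ascertainment.

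Three further points stand. Chart review and telephone collection are also allowed inside the PAS, so the contrast is one of degree. Rupture, SAH and hospitalised SAEs are unlikely to escape a chart. The analysis is descriptive, with no hypothesis attached.

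Two possible answers do not remove the concern. Section 4.9 discusses attrition and uneven participation, with bias possible in both directions, and plans sensitivity analyses on loss to follow-up. It does not separate look-back time from PAS time, and its PAS ITT comparison shares the same gap. The by-interval percentages do not help either: their denominator counts subjects seen during or after the interval, so someone first seen after 3 years enters the 2-year denominator.

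**Conclusion.** The concern holds as a reporting weakness. Table 7 pools two levels of ascertainment without showing it, and probably more than half of the pooled time is the weaker kind. That share rests on planned dates and uniform accrual; actual index dates are not in the documents, and one bounding scenario falls below half.

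The likely direction is low, because look-back misses events more readily than it invents them. The percentage shortfalls are illustrations conditional on an assumed sensitivity and equal true rates in both periods, and cannot be read as an estimate of the bias. Primary 12-month endpoints and success criteria are untouched.

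**What to change.** Keep the pooled Table 7 rate and add to it:

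1. For each safety row, report N1, D1 and the incidence rate separately for (a) the 12-month visit to PAS enrolment, labelled as retrospectively ascertained, and (b) PAS enrolment onward.
2. Give a delayed-entry survival estimate, with entry at PAS enrolment, as a sensitivity analysis.
3. Keep the CEC-adjudicated definition in the main primary-safety row. Report how many gap-period ipsilateral strokes lack a 24-hour NIHSS, and add a sensitivity row that counts them as major.

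The PAS-only rate should not replace the pooled rate. At shares of 55–77% it discards that much person-time, and its interval is roughly 1/√0.45 = 1.5 to 1/√0.23 = 2.1 times wider. With PAS start at 31 March 2020 and last contact at the 3-year visit, only 28.3 − 23.0 = 5.3 months per subject remain on average. The roughly 48% of subjects already at 36 months or more add almost none. Likewise, counting every ungraded stroke as major in the main row would depart from the endpoint definition and push the rate up.

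Cost: Table 7 wording, one date split and a little extra programming, with no new data collection. The PAS-period row will have short person-time and a wide interval, which is why the rows should be shown together.
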